## 1.0 Protocol Summary

Title:	Radial accEss for nAvigation to your CHosen lesion for Peripheral Vascular Intervention: REACH PVI
Study Design:	Prospective, observational, single-arm, multi-center post-market clinical study.
Study Purpose:	The purpose of this study is to prospectively evaluate acute clinical outcomes of orbital atherectomy (OA) via transradial access (TRA) for treatment of peripheral artery disease (PAD) in lower extremity lesions.
Devices:	
This clinical study is designed to collect prospective clinical data on the use of CSI devices cleared for commercial use by the United States Food and Drug Administration (FDA), for the treatment of peripheral artery disease. There will be no investigational devices allowed in this study.
 
Cardiovascular Systems Inc. (CSI) devices may include:
 

• CSI Diamondback 360® Peripheral Orbital Atherectomy System

• CSI Stealth 360® Peripheral Orbital Atherectomy System

• [REDACTED]

Study Population:	All patients undergoing peripheral vascular intervention (PVI) via transradial access (TRA) and for whom TRA has been successfully achieved and peripheral lesion deemed appropriate for treatment via TRA per physician discretion.
Number of Sites:	Up to ten (10) active sites in the United States (U.S.).
Number of Subjects:	Approximately 50 subjects.
Primary Objective:	The objective of this study is to evaluate acute clinical results of orbital atherectomy (OA) via radial artery access, including complication rates and cost effectiveness.
Outcome Measures:	Acute procedure data and device-related data.
Primary Outcome and Secondary Outcome:	
The primary and secondary outcomes will be assessed for all enrolled subjects.
 
Primary Outcome:
 
Procedural Success: Successful completion of OA (orbital atherectomy) treatment of target lesion via transradial access without serious transradial access related events.
 
Secondary Outcome:
 
Treatment Success: Treatment success is defined as <50% residual stenosis post-procedure and without significant angiographic complications without stent placement, or <30% residual stenosis post-procedure and without angiographic complications with stent placement.

	T E
Follow-Up Visits:	All subjects will be followed post-procedure through the first standard of care follow-up visit (7-45 days post-procedure).
Duration:	This study is expected to enroll for approximately 6-12 months. Subjects will be followed through their first standard of care visit.
	T T
Sponsor Contact Information:	Cardiovascular Systems, Inc. (CSI) Clinical Affairs Department – REACH PVI Clinical Study [name] United States [contact]
National Primary Investigator (NPI) Contact Information:	[name] Cardiovascular Institute of the South [REDACTED]

## 2.0 Abbreviations & Definitions

### 2.1 Abbreviations

Abbreviation	Term
AE	Adverse Event
BA	Balloon Angioplasty
BARC	Bleeding Academic Research Consortium
CABG	Coronary Artery Bypass Grafting
CFR	Code of Federal Regulations
CLI	Critical Limb Ischemia
CMP	Clinical Monitoring Plan
CSI	Cardiovascular Systems, Inc.
DS	Diameter Stenosis
DUS	Duplex Ultrasound
eCRF	Electronic Case Report Form
EDC	Electronic Data Capture
FDA	Food and Drug Administration
HIPAA	Health Insurance Portability and Accountability Act
ICF	Informed Consent Form
IFU	Instructions for Use
IRB	Institutional Review Board
MDR	Medical Device Reporting
OA	Orbital Atherectomy
OAS	Orbital Atherectomy System
PAD	Peripheral Artery Disease
PCI	Percutaneous Coronary Interventions
PI	Principal Investigator
PVI	Peripheral Vascular Intervention
QVA	Quantitative Vascular Angiography
RMA	Returned Materials Authorization
RVD	Reference Vessel Diameter
SAE	Serious Adverse Event
SAP	Statistical Analysis Plan
SOC	Standard of Care

SFA	Superficial Femoral Artery
TFA	Transfemoral access
TRA	Transradial Access
TIA	Transient Ischemic Attack
TLR	Target Lesion Revascularization
TVR	Target Vessel Revascularization
US	United States

## 2.2 Definitions

Term	Definition
Adverse Event (AE)	Any untoward medical occurrence, unintended disease or injury or any untoward clinical signs (including an abnormal laboratory finding) in subjects, users or other persons whether or not related to the investigational medical device.
Bleeding (Bleeding Academic Research Consortium, BARC)	
Type 0: No Bleeding
 
Type 1: Bleeding that is not actionable and does not cause the patient to seek treatment
 
Type 2: Any clinically overt sign of hemorrhage that "is actionable" and requires diagnostic studies, hospitalization, or treatment by a health care professional
 
Type 3: a. Overt bleeding plus hemoglobin drop of 3 to < 5 g/dL (provided hemoglobin drop is related to bleed); transfusion with overt bleeding b. Overt bleeding plus hemoglobin drop of < 5 g/dL (provided hemoglobin drop is related to bleed); cardiac tamponade; bleeding requiring surgical intervention for control; bleeding requiring IV vasoactive agents c. Intracranial hemorrhage confirmed by autopsy, imaging, or lumbar puncture; intraocular bleed comprising vision
 
Type 4: CABG-related bleeding within 48 hours
 
Type 5: a. Probably fatal bleeding b. Definite fatal bleeding (overt or autopsy or imaging confirmation)

Dissection Classification	
Type 0: None
 
Type A: Small radiolucent area within lumen of the vessel
 
Type B: Linear, non-persisting extravasation of contrast
 
Type C: Extraluminal, persisting extravasation of contrast
 
Type D: Spiral shaped filling defect
 
Type E: Persistent lumen defect with delayed ante/retrograde flow
 
Type F: Filling defect accompanied by total arterial occlusion
 
Note: Type A,B and C are generally considered benign and minor dissections.

Investigator	Any physician designated and supervised by the Principal Investigator who is participating on the study at the site.
Percent Diameter Stenosis (% DS)	The percent stenosis at minimum lumen diameter as reported using quantitative vascular angiography (QVA) or visual estimation.
Reference Vessel Diameter (RVD)	Defined as the average of normal segments within 10 mm proximal and 10 mm distal to the target lesion from two orthogonal views using QVA or visual estimation.
Rutherford Classification	
Class 0: Asymptomatic; no hemodynamically significant occlusive disease.
 
Class 1: Mild Claudication; there is no limitation with ordinary physical activities (e.g., walking several blocks, climbing stairs). Limiting symptoms may occur with marked exertion (e.g., strenuous, rapid or prolonged exertion at work or recreation).
 
Class 2: Moderate Claudication; there is a slight limitation of ordinary physical activities (e.g., walking uphill, or more than two level blocks, or climbing stairs

Term	Definition
	
rapidly). Patient is comfortable at rest.
 
Class 3: Severe Claudication; there is marked limitation of ordinary physical activities (e.g., walking 1-2 level blocks or climbing one flight of stairs). Patient is comfortable at rest.
 
Class 4: Ischemic rest pain.
 
Class 5: Minor tissue loss, non-healing ulcer, focal gangrene with diffuse pedal ischemia.
 
Class 6: Major tissue loss extending above transmetatarsal level; functional foot no longer salvageable.

Serious Adverse Event (SAE) (ISO 14155 definition)	
a) Led to a death, injury or permanent impairment to a body structure or a body function.
 
b) Led to a serious deterioration in health or the subject, that either resulted in:
 
 
• a life-threatening illness or injury, or
 
• a permanent impairment of a body structure or a body function, or
 
• in-patient hospitalization or prolongation of existing hospitalization, or
 
• medical or surgical intervention to prevent life threatening illness.
 
 
c) Led to foetal distress, foetal death or a congenital abnormality or birth defect.

Procedural Success (per subject)	Procedural success is defined as successful completion of OA (orbital atherectomy) treatment of target lesion via transradial access without serious transradial access related events.
Significant Angiographic Complications	
 
▪ Dissections (D-F)
 
▪ Perforations
 
▪ Serious slow flow/no reflow
 
▪ Serious acute vessel closure
 
▪ Serious distal embolization
 
▪ Serious thrombus formation
 

Target Area	Peripheral arterial anatomy extending from the common femoral artery to the ankle (distal boundary largely dependent on patient height)
Target Lesion	
Stenotic segment appropriate (e.g., location/morphology) for treatment with the Orbital Atherectomy System study device(s) via transradial access.
 
The target lesion will be:
 
 
• The first lesion with Orbital Atherectomy attempted OR
 
• The first lesion with Orbital Atherectomy attempted after other successful peripheral intervention(s) without the occurrence of a reportable adverse event.
 
 
This study will be limited to one (1) target lesion per enrolled subject.

Target Lesion Revascularization (TLR)	A repeat procedure occurring after the index procedure which includes all or part of a target lesion treated during the index procedure.
Target Vessel Revascularization TVR)	A repeat procedure occurring after the index procedure which includes all or part of a target vessel treated during the index procedure.
Target Vessel	The entire vessel in which the target lesion is located.

Term	Definition
Treatment Success (per target lesion)	Treatment success is defined as <50% residual stenosis post-procedure and without significant angiographic complications without stent placement, or <30% residual stenosis post-procedure and without significant angiographic complications with stent placement.

### 3.0 Introduction

Historically, endovascular treatment of coronary and peripheral artery disease has been performed via transfemoral access (TFA). In the past decade, however, access through the radial artery has emerged as a valid alternative approach for percutaneous coronary interventions (PCI) and has significantly decreased the rate of access site bleeding, major vascular complications, and mortality in patients undergoing PCI. Transradial access (TRA) leads to shorter post-procedural monitoring, earlier ambulation, reduced length of hospital stay and less discomfort compared to TFA.

Recent data suggest that TRA may be a safe treatment approach for selected peripheral lesions above-the-knee, especially in patients who are not suitable for TFA, including obese patients, patients with heavily calcified femoral arteries, history of femoral surgery, or in the absence of palpable femoral pulses. The first report on transradial peripheral intervention was published in 2005 and it was a case of a common iliac artery stenting. In the next year, the first report of bilateral iliac artery stenting via TRA performed in the same procedure was published. This is one of the many advantages of TRA, the possibility of the treatment of bilateral lesions in the same procedure without a second access site. Since then, dozens of case reports, feasibility- and single-center studies have been published with high procedural success rates, low rates of access-site and bleeding complications, better patient comfort, and simplified post-procedure care. Studies have shown an increase radiation exposure and longer procedure time compared to TFA. Complications related to TRA are uncommon. Radial artery occlusion is the most significant complication, occurring in 2% to 16% of patients. Other complications include spasm, pseudoaneurysm, nerve damage, perforation, and hematoma. Femoral crossover (1.9%) is another TRA-related incidence and causes include vessel spasm/small vessel diameter, radial loops, proximal occlusion, and catheter length limitations.

Retrospective studies that compared the TRA and TFA in peripheral interventions also demonstrate a comparable safety profile between the two approaches. In a study of 68 subjects with claudication and critical limb ischemia (CLI) who underwent aorto-iliac interventions, there were no minor access-site complications in the TRA group, but 7.3% of the patients had such complications in the TFA group. Furthermore, the time to discharge was significantly shorter for the TRA group compared to the TFA group (14.4 hours vs. 20.9 hours). In their small feasibility study, Cortese et al. reported a 6% major bleeding complication rate for the TFA group compared to 0% in the TRA group. Finally, in a single center study of 188 patients with claudication or CLI who underwent aorto-iliac or femoropopliteal interventions, access site complications occurred in 6% of the TFA patients vs. 3.7% of the TRA patients.

The main barrier to the adoption of TRA is the lack of dedicated equipment with adequate length and small enough outer diameter. Shaft length of balloons and stents needs to be at least 170-180 cm in order to be used for femoropopliteal interventions. Atherectomy devices are limited by both shaft length and outer diameter. The only atherectomy devices that could be used from TRA are the Diamondback 360 Peripheral Orbital Atherectomy System (OAS) and the Stealth 360 Peripheral Orbital Atherectomy System (OAS). This device is the only 6 Fr compatible (4 Fr and 5 Fr with the Micro- and Solid Crowns) atherectomy catheter with shaft lengths of 145 cm - up to 200 cm (longer lengths available for select Solid Crowns).

There are only two case studies that report on OAS use via TRA in the lower extremities. The first study is a case of transradial intervention of severe common femoral artery stenosis with OAS. The intervention was successful, the patient was discharged home four hours after the procedure, and after a month his symptoms disappeared (Rutherford class 0). In the second study, Hanna and colleagues treated 6 patients

with superficial femoral artery (SFA) disease with OAS and adjunctive balloon angioplasty (BA) via TRA. They concluded that for simple SFA disease stand-alone transradial recanalization is feasible and may be performed with high success rate.

The objective of this study is to evaluate acute clinical results of orbital atherectomy (OA) via radial artery access including complication rates and cost effectiveness.

## **4.0 Risks and Benefits**

### **4.1 Risks**

All devices that will be used in this study have been cleared or approved by FDA. Clinical risks to subjects enrolled in this study are the same risks encountered if treated outside of the study. The choice of treatment for enrolled subjects will be determined by the Investigator. The Investigator should refer to the manufacturer's Instructions for Use (IFU) for each technology used in the study for specific device related risks, contraindications, restrictions, warnings and precautions.

Since this study will enroll subjects who otherwise would be indicated for treatment, the pre-procedure preparation and follow-up care will be the same and do not present different risks from those not participating in the study. Subjects may undergo additional tests per the Investigator's discretion if he/she desires to monitor the subject's disease state more closely.

### **4.2 Benefits**

Subject's participation in this study is voluntary. There is no direct additional benefit to subjects enrolled in the study. However, information gathered from this study may help increase the understanding of the clinical and economic outcomes of transradial access with lower extremity PAD. Ultimately, this knowledge can inform future PAD clinical trials, provide data to help physicians choose the best care for patients, and advance the knowledge of transradial access for treatment of lower extremity PAD.

## **5.0 Devices Used in Study**

This clinical study is designed to evaluate OAS use via TRA. Only endovascular devices cleared or approved for commercial use by the FDA can be used in this study, please refer to the appropriate device-specific IFU. There will be no investigational devices allowed in this study.

Cardiovascular Systems Inc. (CSI) devices designed for use via TRA include:

- CSI Diamondback 360® Peripheral Orbital Atherectomy System
- CSI Stealth 360® Peripheral Orbital Atherectomy System
- [REDACTED]

## **6.0 Study Objective**

The objective of this study is to evaluate acute clinical results of orbital atherectomy (OA) via radial artery access, including complication rates and cost effectiveness.

## **7.0 Outcome Measures**

The primary and secondary outcomes will be assessed for all enrolled subjects.

## 7.1 Primary Outcome: Procedural Success

Procedural success is defined as successful completion of OA treatment of the target lesion via transradial access without serious transradial access related events.

## 7.2 Secondary Outcome: Treatment Success

Treatment success is defined as <50% residual stenosis post-procedure and without significant angiographic complications without stent placement, or <30% residual stenosis post-procedure and without significant angiographic complications with stent placement.

## 8.0 Sample Size

Approximately 50 subjects treated with OA will be enrolled in this study. As a hypothesis generating study, this study is not powered.

Subjects must meet ALL of the inclusion criteria and NONE of the exclusion criteria to be eligible to participate in this study. Subject will be approached and consented for participation in the study prior to the index procedure, during which index inclusion and exclusion criteria will be confirmed. Subjects found to not meet index inclusion criteria or to meet index exclusion criteria will be considered consented screen failures.

## 9.0 Study Enrollment

### 9.1 General Inclusion Criteria

1. Subject is  $\geq$  18 years
2. Subject is willing and able to sign the IRB-approved informed consent form (ICF)
3. Subject presents with a Rutherford Classification of 2 to 5
4. Subject has a positive Allen's Test
5. Subject to undergo peripheral angiography and/or PVI via TRA approach per physician discretion

### 9.2 Index Procedure Inclusion Criteria

1. Physician obtains successful radial artery access (Note: snuffbox access is allowed)
2. Target lesion appropriate (i.e. location/morphology) for OA treatment via TRA within target area
3. OAS use attempted (defined as ViperWire introduced into the body)

### **9.3 General Exclusion Criteria**

1. Subject has no palpable radial artery on the planned access arm
2. Subject has a previous failed radial access attempt on planned access arm
3. Subject has a dialysis fistula on planned access arm
4. Subject has a known subclavian stenosis or occlusion
5. Subject has a previous subclavian stent or previous subclavian intervention
6. Subject has a shunt in the radial artery on the planned access arm
7. Subject has evidence of osteomyelitis
8. Subject is currently participating in an investigational drug or device study
9. Subject is pregnant within the study period

### **9.4 Index Procedure Exclusion Criteria**

1. Physician unable to obtain radial artery access
2. Physician determines TRA is not acceptable due to patient anatomy, lesion characteristics, and/or disease severity
3. OAS use not attempted (defined as ViperWire introduced into the body)

**Prior to insertion of ViperWire:**

4. Femoral access is obtained
5. Unsuccessful peripheral intervention
6. A reportable adverse event has occurred

[figure not shown]
### **9.5 Treatment of Target Lesion**

The target lesion will be:

- The first lesion with Orbital Atherectomy attempted OR
- The first lesion with Orbital Atherectomy attempted after other successful peripheral intervention(s) without the occurrence of a reportable adverse event.

### **9.6 Point of Enrollment**

Enrollment is defined as point when a subject has signed an IRB-approved ICF, have met all inclusion criteria and none of the exclusion criteria, and the ViperWire has been inserted into the body.

## 11.0 Follow-Up Visit

All subjects will be followed post-procedure through the first standard of care follow-up visit (7-45 days post-procedure) only.

## 13.0 Adverse Event

### 13.1 Adverse Event Collection

The reporting of adverse events (AEs) will begin immediately after the subject has been enrolled. For the purposes of this study, pre-planned interventions noted at baseline are not considered reportable AEs. The AEs collected in this study will include:

**TRA Related Events** are defined for the purpose of the data analyses of the study's outcome and include access site complications such as:

- Serious TRA site bleeding (BARC Type 2-5)
- Serious TRA site hematoma
- Serious radial artery spasm
- Serious hand ischemia
- Stroke
- Transient Ischemic Attack (TIA)
- Serious nerve damage
- Perforation
- TRA site pseudoaneurysm

**Significant Angiographic Events** that occur during the treatment procedure regardless of device relatedness including:

- Dissections (D-F)
- Perforations
- Serious slow flow/no reflow
- Serious acute vessel closure
- Serious distal embolization
- Serious thrombus formation

[REDACTED]

i [REDACTED]

### 13.2 Adverse Event Definitions

**Serious Adverse Event (SAE)** means:

- a) Led to a death, injury or permanent impairment to a body structure or a body function.
- b) Led to a serious deterioration in health or the subject, that either resulted in:
  - a life-threatening illness or injury, or
  - a permanent impairment of a body structure or a body function, or
  - in-patient hospitalization or prolongation of existing hospitalization, or
  - medical or surgical intervention to prevent life threatening illness.
- c) Led to foetal distress, foetal death or a congenital abnormality or birth defect.

**Permanent** means irreversible impairment or damage to a body structure or function, excluding trivial impairment or damage.

**Medical interventions** may include hospitalizations or prolonged hospitalizations due to the use of the interventional devices used in this study.

**Device related** means related to any CSI device used during index procedure on the target lesion.

**Access Site Bleeding:** Bleeding Academic Research Consortium, BARC. Access site BARC Type 2 – Type 5 bleeding events that occur during the index procedure through study exit will be collected.

Type 0: No Bleeding

Type 1: Bleeding that is not actionable and does not cause the patient to seek treatment

Type 2: Any clinically overt sign of hemorrhage that “is actionable” and requires diagnostic studies, hospitalization, or treatment by a health care professional

Type 3: a. Overt bleeding plus hemoglobin drop of 3 to < 5 g/dL (provided hemoglobin drop is related to bleed); transfusion with overt bleeding  
b. Overt bleeding plus hemoglobin drop of < 5 g/dL (provided hemoglobin drop is related to bleed); cardiac tamponade; bleeding requiring surgical intervention for control; bleeding requiring IV vasoactive agents  
c. Intracranial hemorrhage confirmed by autopsy, imaging, or lumbar puncture; intraocular bleed comprising vision

Type 4: CABG-related bleeding within 48 hours

Type 5: a. Probably fatal bleeding

b. Definite fatal bleeding (overt or autopsy or imaging confirmation)

[figure not shown]

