7.4 Primary Outcome Measure Analysis

Analysis of the primary outcome measure of Procedural Success will be assessed post-procedure on the ITT analysis set. Procedural Success is comprised of:

- Successful completion of OA treatment via transradial access determined by use of the device within the target lesion
- The presence of no serious transradial access related events. TRA related events include:
 - Serious TRA site bleeding (BARC Type 2-5)
 - Serious TRA site hematoma
 - Serious radial artery spasm
 - Serious hand ischemia
 - Stroke
 - Transient Ischemic Attack (TIA)
 - Serious nerve damage
 - Perforation
 - TRA site pseudoaneurysm

Procedural Success is considered successful for a subject if all criteria are met.

A large rectangular area of the page is completely blacked out, indicating redacted content. It is positioned below the 'Procedural Success' text and above the page footer.

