7.8 Adverse Event (AE) Rates

Adverse event rates will be assessed on the ITT analysis set. All reportable adverse events specified in the protocol will be included in the analysis. Adverse events are collected starting at enrollment through subject exit from the study. AEs will be summarized by AE term and overall for number and percent of subjects experiencing each event, and number of events. AEs will also be summarized by AE category.

Adverse events summaries will be provided through study exit in the following groups:

- Serious Adverse Event (SAE): Any AE that meets the protocol definition of serious

Any events for which the determination of seriousness and/or relatedness to the device cannot be determined will count as serious and/or related for the purposes of this analysis.

No further analyses are planned outside those outlined in **Section 7 Required Data Analyses**. Any ad hoc analyses will follow the guidelines outlined in this document.

Page 11 of 11

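### The Type 3b hemoglobin threshold in the Protocol's bleeding scale swallows Type 3a and leaves drops of 5 g/dL or more with no hemoglobin criterion

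*Protocol*

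**What the plan says.** The Protocol prints the BARC bleeding scale twice, in 2.2 (Definitions) and in 13.2 (Access Site Bleeding). In 13.2 the hemoglobin criterion for Type 3a is "Overt bleeding plus hemoglobin drop of 3 to < 5 g/dL", and for Type 3b it is "Overt bleeding plus hemoglobin drop of < 5 g/dL (provided hemoglobin drop is related to bleed". The copy in 2.2 gives 3b the same threshold: "Overt bleeding plus hemoglobin drop of < 5 g/dL". In both places the drop must be related to the bleed. Type 3a can also be met by transfusion, and Type 3b by tamponade, surgical control or intravenous vasoactive drugs.

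Two lower grades matter here. Type 1 is "Bleeding that is not actionable and does not cause the patient to seek treatment". Type 2 is an actionable overt bleed that "requires diagnostic studies, hospitalization, or treatment by a health care professional".

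The scale is used in three places:

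- **Collection.** Protocol 13.2 says that access-site BARC Type 2 to 5 "bleeding events that occur during the index procedure through study exit will be collected".
- **Primary outcome.** SAP 7.4 lists "Serious TRA site bleeding (BARC Type 2-5") among the events that make Procedural Success fail. Protocol 13.1 has the same list.
- **AE rates.** SAP 7.8 says "AEs will be summarized by AE term and overall for number and percent of subjects experiencing each event, and number of events". It adds summaries by AE category and for serious events.

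**The concern.** In an ordered scale, 3b should need a larger drop than 3a. Here both share the upper limit of 5 g/dL and 3b has no lower limit. A bleed with a related drop of 1 g/dL meets 3b. An actionable bleed with a drop of 6 g/dL and no other Type 3 criterion is only Type 2. The smaller bleed therefore gets the higher grade.

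The scale decides which access-site bleeds are collected at all, and it feeds the primary outcome. A wrong threshold could therefore change which events are recorded, the AE rates and Procedural Success, as well as any report of bleeding by subtype.

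**Working it through.** The study is not powered and the plan states no figure that depends on this threshold, so there is no plan figure to reproduce. The check is one of logic.

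**Step 1: the hemoglobin criteria alone.** The thresholds come from Protocol 2.2 and 13.2. The last column is a comparison reading in which 3b starts where 3a ends. It is inferred from the upper limit of 3a and is not stated in the documents.

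| Related drop (g/dL) | 3a | 3b as written | 3b starting at 5 |
|---|---|---|---|
| above 0, below 3 | no | yes | no |
| 3 to below 5 | yes | yes | no |
| 5 or more | no | no | yes |

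**Step 2: does the error reach the pooled BARC 2-5 group?** A bleed is in the group if it meets any criterion of Type 2 or higher. No rule for ranking types is needed.

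- *Actionable bleed, any drop:* already Type 2, so it is in the group under both readings.
- *Another Type 3 criterion met (transfusion, surgery and so on):* in the group under both readings.
- *Non-actionable, no other Type 3 criterion, drop of 3 to below 5:* in the group through 3a under both readings.
- *Non-actionable, no other Type 3 criterion, drop above 0 and below 3:* in the group as written (3b), out under the comparison reading (Type 1). **Changes.**
- *Non-actionable, no other Type 3 criterion, drop of 5 or more:* out as written, in under the comparison reading. **Changes**, although such a large drop with no action taken is improbable.

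**Step 3: enumeration as a cross-check.** Take drops of 0, 0.5, 2, 2.9, 3, 4.9, 5 and 7 g/dL. Cross them with actionable or not, transfusion or not, and surgery/tamponade/vasoactive drugs or not, with transfusion and the latter group taken to imply actionable. That leaves 1 non-actionable and 4 actionable combinations per drop: 8 × 5 = 40 profiles, 8 non-actionable and 32 actionable.

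- Both 3a and 3b met, as written: 1 (drop 0) + 6 (0.5, 2, 2.9) + 10 (3, 4.9) + 2 (5, 7) = 19.
- Both met, with 3b starting at 5: 1 + 3 + 4 + 4 = 12. These come from the non-hemoglobin criteria.
- BARC 2-5 membership differs in 0 of 32 actionable and 5 of 8 non-actionable profiles: 0.5, 2 and 2.9 enter as written, 5 and 7 leave.
- If the highest type met is taken as the grade (a rule the visible documents do not state), the grade differs in 21 profiles, and 21 − 5 = 16 of these stay within BARC 2-5.

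The counts depend on the drops chosen. They are not frequencies.

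**Step 4: weight of one subject.** With N = 50 (Protocol 8.0, approximate), one more failure costs 1/50 = 2.0 percentage points. For example, 50/50 = 100% (95% CI 92.9 to 100) becomes 49/50 = 98.0% (89.4 to 99.9). The intervals are exact Clopper-Pearson. The SAP gives alpha 0.05, but its visible text names no interval method.

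**The case against.** The strongest reply is that this is a slip in one comparison sign with almost no planned consequence. The primary outcome pools BARC 2-5, no visible table splits 3a from 3b, and the study is hypothesis-generating. The remaining route needs several conditions at once: an overt, non-actionable bleed, a related drop under 3 g/dL, and a hemoglobin test done for some other reason, since a test prompted by the bleed arguably makes it Type 2. For the primary outcome, *Serious* must also be defined by BARC 2-5 alone. If it is a further filter using the SAE definition, a bleed that needed no action would rarely qualify. All of this stands and is why the point is minor.

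Three further objections have some force:

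- **The 2.0 points** are what any single failure costs at N = 50. They give the weight of one event, not the size of this error.
- **Graders may have had other material.** The Protocol names the scale, and the CRFs, which are not available here, may carry correct grading options. That could soften the effect in practice. It does not correct the Protocol, whose 24 references include no title that is a BARC definition.
- **A re-check cannot recover bleeds that were never collected.** It can find bleeds wrongly included and correct subtypes. It cannot find those left out because they were graded below Type 2.

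A PDF-reading fault is unlikely: the same sign appears in a table and in body text, and a greater-than-or-equal sign was read correctly in Protocol 9.1.

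**Conclusion.** The concern holds. The 3a and 3b hemoglobin criteria cannot both be right in an ordered scale, and the fault is in both copies. It is an error in an operative definition, with minor analytic effect.

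In the visible analyses only non-actionable overt bleeds with no other Type 3 criterion can change status. In practice these are bleeds that would otherwise be Type 1, with an incidentally measured related drop under 3 g/dL. As written they are collected and enter the AE rates. They also count against Procedural Success if BARC 2-5 alone defines *Serious*, at 2.0 points each.

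How often this would happen cannot be estimated: the documents give no rate for such bleeds, and no visible text says whether hemoglobin is tested routinely (Protocol Sections 10 and 12 are not visible). If a redacted SAP section tabulates BARC subtypes, the overlap would matter more there. Confidence is high for the inconsistency. An effect on the results is possible but not shown.

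**What to change.** In Protocol 2.2 and 13.2, reconcile the two hemoglobin criteria so that they do not overlap, leave no gap at the top, and make 3b the more severe. The upper limit of 3a implies that 3b starts at 5 g/dL or more. That is an inference, so the sponsor should confirm it against its BARC source and add the source to the references. The CRF grading options should be checked for the same wording.

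Re-check any bleeds already graded, looking first for collected events whose only qualifying criterion was a drop under 3 g/dL. State that bleeds graded below Type 2 may not be recoverable from the study data.

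The cost is a few words in two sections, one citation and a short review of graded bleeds. No sample size or alpha is affected.
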